12.1 Dose Limiting Toxicities

The number of DLTs will be summarized by treatment arms for the DLT Evaluable Population. A toxicity will be considered a DLT if it occurs from the first dose to the end of Cycle 1 (including the PK evaluation period), meets the pre-defined criteria for DLTs, is deemed at least possibly related to trial treatment, and is not clearly and incontrovertibly due to disease progression or extraneous cause. Toxicity will be assessed using CTCAE v 5.0, unless other specified. Details of DLTs will be listed.

DLTs will be defined as any of the following:

Any death not clearly due to the underlying disease or extraneous causes

Hematologic TEAES:

- Grade 4 neutropenia
- Febrile neutropenia (defined as absolute neutrophil count (ANC) <1000 cells/ μ L with a single temperature of 38.3°C [100.4°F] for > 1 hour).
- Grade 4 thrombocytopenia or Grade 3 thrombocytopenia associated with Grade \geq 2 bleeding.
- Grade 4 anemia or Grade 3 anemia requiring red blood cell (RBC) transfusion given to participants with documented anemia-related symptoms.

Non-Hematologic TEAEs:

- Any Grade \geq 3 TEAE except the below
 - 1. Grade ≥ 3 non-hematologic laboratory abnormalities that are asymptomatic and respond to medical intervention or resolve to grade 1 in \leq 72 hours.
 - 2. Grade 3 fatigue with duration < 7 days
 - 3. Grade \geq 3 nausea/vomiting/diarrhea that lasts \leq 72 hours and resolves with or without optimal supportive care.
 - 4. Grade \geq 3 amylase or lipase elevation not associated with symptoms or clinical manifestations of pancreatitis.
 - 5. The use of red blood cell transfusion for anemia Grade <3 or the use of G-CSF for Grade <4 neutropenia
- Symptomatic Grade ≥ 3 QTc prolongation (QTcF ≥ 501 msec on at least two separate electrocardiogram (ECGs)), or asymptomatic Grade ≥ 3 QTc prolongation that has been confirmed by repeat testing and reevaluation by a qualified person and persists after correction of reversible causes such as electrolyte abnormalities or hypoxia.
- Drug-induced liver injury meeting Hy's Law criteria defined as:
 - 1. ALT or AST ≥3-fold above the Upper Limit of Normal (ULN) or 5.0 x ULN in the case of liver metastases at baseline and
 - 2. Serum total bilirubin \geq 2-folde above ULN (without findings of cholestasis) and
 - 3. Alkaline phosphatase $\leq 2 \times ULN$ and
 - 4. No other overt reason for liver injury

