14.1.1 Schedule of Activities

Table 1 Schedule of Activities for Participants Enrolled on 2 Weeks On/1 Week Off Dosing (21-Day Cycles)

						Cyc	e 0														
	Pre- screening						Food Effect or ing Cohorts							Cycle 2			Additional Cycles		EOT/ ET°	Safety	Survival Follow- up ^e
		Screening ^a	Ef For	d (Fo fect) mula l (Pl ridgi	or ation K	Ef Forn	Fasted (Food Effect) or Formulation 2 (PK Bridging)					Cycle	1							Follow -up Visit ^d	
Trial Days	-180 to -1	-28 to -1	1ª	2	3 4	5 (+5)	6	7	8	1ª	1	8 (+2)	15 (+2)	1 (+3)	8 (+2)	15 (+2)	1 (+3) ^g	8 (+2) ^h	Within +7 days of Disc of	30 days after last	Every 90 days (±14 days)
Procedures/ Assessments ^f																			Trt date	dose (+14 days)	
Pre-screen informed consent	X																				
Screening/mai n informed consent		X																			
Inclusion/ exclusion criteria		X	X							X											

	Pre- screening	Screeninga				Cycl	e 0														
			PK	PK Cycle For Food Effe PK Bridging Cohor						PK Cycle ^b									EOT/	Safety Follow	Survival
			Ef For	d (Fo fect) mula 1 (PK ridgin	or tion	Fasted (Food Effect) or Formulation 2 (PK Bridging)				Fasted		Cycle	e 1	Cycle 2				tional cles	EO17	-up Visit ^d	Follow- up ^e
Trial Days	-180 to -1	-28 to -1	1ª	2	3 4	5 (+5)	6	7	8	1ª	1	8 (+2)	15 (+2)	1 (+3)	8 (+2)	15 (+2)	1 (+3) ^g	8 (+2) ^h	Within +7 days of Disc of Trt	30 days after last	Every 90 days (±14 days)
Procedures/ Assessments ^f																			date	dose (+14 days)	
Molecular eligibility ⁱ	X																				
Demographics	X																				
Medical/cance r history		X																			
Physical examination		X	X							X									X		
Abbreviated PE ^j														\mathbf{X}^{j}			\mathbf{X}^{j}			X	
Height ^k		X															X^k				
Weight		X	X							X				X			X		X	X	
Vital sign measurements ¹		X	X							X	X	X	X	X	X	X	X	X ^h	X	X	

							Cycle	e 0														
	-		PK	Cy PK	/cle K Br	For idgi	· Food I ing Coh	Effe	ct o	r	PK Cycle ^b							Additional		EOT/	Safety	Survival
	Pre- screening	Screening ^a	E1 For B1	1 (P ridg	t) or latio 'K jing)	Fasted (Food Effect) or Formulation 2 (PK Bridging)				Fasted		Cycle	:1	Cycle 2				tional cles	ET°	Follow -up Visit ^d	Follow- up ^e	
Trial Days	-180 to -1	-28 to -1	1ª	2	3	4	5 (+5)	6	7	8	1 ^a	1	8 (+2)	15 (+2)	1 (+3)	8 (+2)	15 (+2)	1 (+3) ^g	8 (+2) ^h	Within +7	30 days	Every 90 days
Procedures/ Assessments ^f																				days of Disc of Trt date	after last dose (+14 days)	(±14 days)
ECOG or Lansky performance status		X	X								X				X			X		X	X	

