- ff. Post-trial Therapy Data Collection: All anticancer therapies with start and stop dates should be recorded for 6 months after treatment discontinuation.

	 	

Table 3: Schedule of Activities for Participants Enrolled on a 3 Days On/4 Days Off Dosing (RP-1664 Days 1-3, 8-10, 15-17: 21-Day Cycles; if Needed)

							Cycle 0																	
	Pre-	Screening ^a	PI	K Cy	cle fo Brid	or Foo ging (d Effect Cohorts	or P	K		PK Cycl			Cycle	. 1			Cycle 2		Addi	tional	EOT/	Safety Follow-	Survival Follow-
	screening	Screening	or I	(Foo Form K Br	ulati		Faste Effe Form (PK F	ect) (ulati	or on 2	1	Fast	ed		Cycle	. 1			yele 2		Cy	cles	ET°	up Visit ^d	upe
Trial Days Procedures/ Assessmentsf	-180 to -1	-28 to -1	1ª	2	3	4	5 (+5)	6	7 8	8 1	1 ^a	2	1	8 (+2)	15 (+2)	1 (+1)	3	10 (+2) ^g	17 (-1)	1 (+3) ^h	8 (+2) ⁱ	Within +7 days of Disc of Trt date	30 days after last dose (+14 days)	Every 90 days (±14 days)
Pre-screen informed consent	X																							
Screening/main informed consent		X																						
Inclusion/ exclusion criteria		X	X								X													
Molecular eligibility ^j	X																							
Demographics	X																							
Medical/cancer history		X																						
Physical examination		X	X								X											X		

							Cycle 0)		K PK													
	Pre-	Screening ^a	PI				d Effec Cohorts		'K		K cle ^b		Cycle	. 1		(Cycle 2		Addi		EOT/	Safety Follow-	Survival Follow-
	screening	Screening	or I	orm	od Ef ulati idgir	on Í	Faste Eff Form (PK 1	fect) (lulati	or on 2	Fas	sted		Cych	. 1			yele 2		Cy	cles	ETe	up Visit ^d	up ^e
Trial Days Procedures/	-180 to -1	-28 to -1	1ª	2	3	4	5 (+5)	6	7 8	1ª	2	1	8 (+2)	15 (+2)	1 (+1)	3	10 (+2) ^g	17 (-1)	1 (+3) ^h	8 (+2) ⁱ	Within +7 days of Disc of Trt date	30 days after last dose (+14	Every 90 days (±14 days)
Assessments ^f Abbreviated PE ^k															X ^k				X ^k			days) X	
Height ^l		X																	X ^l				
Weight		X	X							X					X				X		X	X	
Vital sign measurements ^m		X	X							Х		X	X	X	X		X	X	X	Xi	X	X	
ECOG or Lansky performance status		X								Х					X				X		X	X	
12-lead ECG ⁿ		X	X				X			X			X			X			X				
Pregnancy test ^o		X	X				_			X					X				X		X	X	
Clinical safety lab tests ^p		X	X							X					X				X		X	X	
CBC with diff (included in safety lab tests)													X	X			X	X		Xi			
ctDNA whole blood ^q		X	X							X				X				X	X	Xi	X		

							Cycle ()																

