Post-trial therapy data collection ^{gg}																								X
Survival status																								X

- a. **Screening:** Screening Period extends from Day -28 to Day -1. Screening assessments may be used as Cycle 0 Day 1 assessments if performed within 96 hours of the first dose of RP-1664, except for the ctDNA blood draw, vital signs, and ECGs. ECOG or Lansky performance status and PE that are completed within 24 hours of first dose of RP-1664 may be used as Cycle 0 Day 1 assessments. Participants must continue to meet eligibility criteria prior to first dose of RP-1664 on Cycle 0 Day 1.
- b. Cycle 0: The 2-day PK Cycle 0 is not required for participants in the food effect or PK bridging portion of the trial.
- c. **EOT/ET:** A post-treatment/ET visit will be conducted following the last dose of trial intervention and within 7 days after the date of treatment discontinuation but prior to the start of the next anticancer therapy.
- d. Safety Follow-Up: Required for all participants who discontinued from the trial for whatever reason.
- e. **Survival Follow-Up:** Survival follow-up will be conducted approximately every 90 days (±14 days) after date of treatment discontinuation until the end of trial (for up to 6 months), participant withdrawal of consent to trial, or death. This follow-up may be conducted by telephone contact or standard method used by participating centers and agreed by the Sponsor.
- f. **Procedures/Assessments:** Pre-screening for molecular eligibility can take place up to 180 days before first dose of RP-1664. Screening procedures and tumor assessment must be performed within 28 days before first dose of RP-1664.
- g. Day 10 of Cycle 2: Labs and vital signs can be done locally at these timepoints as long as they are reviewed by the research team on the day of draw.
- h. **CXD1:** The start of a new additional cycle should always coincide with the start of trial drug administration for that cycle. A +3-day window is allowed for the start of new cycles, though cycles should never start early and should be at least 21 days in length. A -2-day window is allowed for the assessments scheduled for the CXD1 visit to enable flexibility with visit scheduling.

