- i. **Day 8 of Additional Cycles:** CBC and vital signs to be assessed only on C3D8 and not thereafter. Labs and vital signs can be done locally as long as they are reviewed by the research team on the day of draw. For Cycle 3, ctDNA should be collected on Day 8 and not on Day 1, however for Cycles 4 and up, ctDNA should be collected on Day 1. Blood samples for 4β-OHC and total cholesterol are only collected up to Cycle 3.
- j. **Molecular Eligibility:** NGS, FISH, or SNP microarray reports will be emailed for central review to confirm molecular eligibility or determine if additional testing is required.
- k. Abbreviated PE: Starting at Cycle 2, abbreviated PE to be performed every 2 cycles (unless full PE necessary by Investigator judgment).
- 1. **Height:** Pediatric participants will have their height measured every 3 cycles.
- m. Vital Signs: Blood pressure, heart rate, and temperature to be measured after the participant has been sitting for 5 minutes.
- n. ECG: 12-lead ECGs to be done in triplicate ≥ 1 minute apart per Table 4. The triplicate ECG measurements must occur within a 30 minute time period. Participants should be in supine position and resting for at least 10 minutes before trial-related ECGs. QTcF should be recorded (QTcB is not required). Participants in the food effect or PK bridging portion of the trial should have ECGs collected per Table 11 and Table 12, respectively.
- o. **Pregnancy Test**: For women of childbearing potential, a serum pregnancy test is required at Screening. If pregnancy test was done within 96 hours of Cycle 0 Day 1, repeat testing is not required. A serum or urine pregnancy test must be performed on Day 1 of each cycle starting on Cycle 2, at EOT, and at Safety Follow-up visit. A pregnancy test can be performed more frequently if required per local regulations.

у.

- p. Clinical Safety Laboratory Tests: Clinical laboratory tests (including serum or plasma chemistry, hematology [including reticulocyte count], and urinalysis) will be performed at local laboratories according to the laboratory's normal procedures. See Section Error! Reference source not found. for a complete listing of laboratory tests to be performed.

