- dd. **Tumor Assessment:** Tumor assessments by disease-appropriate standard criteria (e.g., RECIST v1.1 or INRC) using CT/MRI of known sites of disease as clinically indicated. Tumor assessments must be performed at Screening and every 6 weeks (±7 days) from C1D1 for the first 3 assessments, or sooner if clinically indicated). Thereafter, assessments must be performed every 9 weeks (±7 days). Per RECIST v1.1, complete response or partial response should be confirmed; tumor imaging for confirmation of response must be performed at least 4 weeks after the first indication of response. The subsequent tumor imaging after the confirmation of response should be obtained per the original scheduled interval from the confirmatory scan (6 weeks ± 7 days during the first ~5 months of trial treatment or every 9 weeks thereafter). If a participant discontinues treatment for a reason other than radiographic disease progression, withdrawal of consent to trial, lost to follow-up, or death, scans should continue at the specified intervals until progression is confirmed or until start of subsequent anticancer treatment. All radiographic images/scans at the timepoints specified as well as any unscheduled images/scans should be archived by the trial sites for potential future evaluation.
- ee. **Tumor Assessment at Screening**: Scans performed prior to signing of the ICF as part of routine clinical management are acceptable for use as baseline tumor imaging if they are of diagnostic quality and performed within 28 days prior to the first dose on Cycle 0 Day 1.
- ff. **Serum Tumor Markers:** This assessment applies only to participants with cancers being monitored by circulating tumor markers (e.g., CA-125 or PSA). The baseline assessment should be performed within 96 hours of the first dose on Cycle 0 Day 1. If the assessment is done during Screening prior to this time, it should be repeated within the allotted time frame. It should then be collected on Day 1 of each subsequent cycle starting at Cycle 2, or per standard of care, through end of treatment.
- gg. Post-trial Therapy Data Collection: All anticancer therapies with start and stop dates should be recorded for 6 months after treatment discontinuation

Table 5: Schedule of Activities for Participants Enrolled on Daily Dosing (21-Day Cycles; if needed)

							Сус	le 0															
	Pre-	Screening ^a]	PK C			ood Ef		or PK		Pi Cyc			Cycle	. 1		Cycle 2			tional	EOT/	Safety Follow-	Survival Follow-

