- cc. **Tumor Assessment:** Tumor assessments by disease-appropriate standard criteria (e.g., RECIST v1.1 or INRC) using CT/MRI of known sites of disease as clinically indicated. Tumor assessments must be performed at Screening and every 6 weeks (±7 days) from C1D1 for the first 3 assessments, or sooner if clinically indicated). Thereafter, assessments must be performed every 9 weeks (±7 days). Per RECIST v1.1, complete response or partial response should be confirmed; tumor imaging for confirmation of response must be performed at least 4 weeks after the first indication of response. The subsequent tumor imaging after the confirmation of response should be obtained per the original scheduled interval from the confirmatory scan (6 weeks ± 7 days during the first ~5 months of trial treatment or every 9 weeks thereafter). If a participant discontinues treatment for a reason other than radiographic disease progression, withdrawal of consent to trial, lost to follow-up, or death, scans should continue at the specified intervals until progression is confirmed or until start of subsequent anticancer treatment. All radiographic images/scans at the timepoints specified as well as any unscheduled images/scans should be archived by the trial sites for potential future evaluation.
- dd. **Tumor Assessment at Screening:** Scans performed prior to signing of the ICF as part of routine clinical management are acceptable for use as baseline tumor imaging if they are of diagnostic quality and performed within 28 days prior to the first dose on Cycle 0 Day 1.
- ee. **Serum Tumor Markers:** This assessment applies only to participants with cancers being monitored by circulating tumor markers (e.g., CA-125 or PSA). The baseline assessment should be performed within 96 hours of the first dose on Cycle 0 Day 1. If the assessment is done during Screening prior to this time, it should be repeated within the allotted time frame. It should then be collected on Day 1 of each subsequent cycle starting at Cycle 2, or per standard of care, through EOT.
- ff. Post-trial Therapy Data Collection: All anticancer therapies with start and stop dates should be recorded for 6 months after treatment discontinuation.

[figure not shown]

Table 7: Schedule of Activities for Participants Enrolled on 1 Week On/1 Week Off Dosing (28-Day Cycles, if Needed)

				K Cycle For Foo Bridging (Fed (Food Effect) or			cle 0																

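### On the 3 days on/4 days off schedule, no scheduled ECG in the DLT window is required to follow consecutive-day dosing

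*SAP*

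**What the plan says.** The title of Table 3 in SAP 14.1.1 gives the dosing calendar: "3 Days On/4 Days Off Dosing (RP-1664 Days 1-3, 8-10, 15-17: 21-Day Cycles; if Needed". The 12-lead ECG row of that table is marked at Screening, Cycle 0 Day 1 (and Cycle 0 Day 5 for food-effect and bridging participants), Cycle 1 Day 8 (+2), Cycle 2 Day 3, and Day 1 of additional cycles. Cycle 1 Day 1 and Day 15 carry no mark. Footnote n sets the detail: "12-lead ECGs to be done in triplicate ≥ 1 minute apart per Table 4". Table 4 is not reproduced in the public text.

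SAP 12.1 counts a toxicity as a DLT if it "occurs from the first dose to the end of Cycle 1 (including the PK evaluation period") and meets the listed criteria. One criterion is "asymptomatic Grade ≥ 3 QTc prolongation that has been confirmed by repeat testing" and that persists once reversible causes are corrected. Symptomatic Grade 3 or higher prolongation also counts.

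In the other schedules the single Cycle 1 ECG is at Day 8 (+2) in Tables 1, 5 and 9, and at Day 7 (-1) in Table 7.

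**The concern.** Day 8 means different things in different schedules. In Tables 1, 5 and 9 it comes after a week of daily dosing. In Table 3 it is the first dose after Days 4 to 7 off. The Cycle 0 ECGs surround single doses, so none of the ECGs that Table 3 schedules inside the DLT window has to follow consecutive-day dosing.

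The asymptomatic QTc criterion can be met only if an ECG is taken. If a QTc effect needs accumulation, the scheduled ECGs on this schedule could miss it in the window that decides whether a dose level is cleared. Clearance has wider effects: the Protocol synopsis lets other participants change to doses and schedules that have been cleared for DLT evaluation.

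Table 3 already uses the third dosing day elsewhere. Its Cycle 2 ECG is on Day 3, and its on-treatment biopsy (footnote s) is on Cycle 2 Day 17. Only the Cycle 1 ECG column is out of step with the short dosing block.

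**Working it through.** **Step 1: the calendar.** Three days on and four off over 21 days gives dosing on Days 1, 2, 3, 8, 9, 10, 15, 16 and 17, which reproduces the Table 3 title. Days 4–7, 11–14 and 18–21 are off.

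**Step 2: the ECG marks.** Column alignment in Table 3 was checked against the Weight row, whose marks fall where expected (Screening, Cycle 0 Day 1, Cycle 2 Day 1, Day 1 of additional cycles, EOT, Safety Follow-up). Consecutive daily doses up to and including the Cycle 1 ECG day are:

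| Schedule | Cycle 1 ECG | Consecutive doses |
|---|---|---|
| Table 3, 3 on/4 off | Day 8 (+2) | 1 on Day 8, 2 on Day 9, 3 on Day 10 |
| Table 1, 2 weeks on/1 off | Day 8 (+2) | 8 to 10 |
| Table 5, daily | Day 8 (+2) | 8 to 10 |
| Table 7, 1 week on/1 off | Day 7 (-1) | 6 or 7 |
| Table 9, 2 weeks on/2 off | Day 8 (+2) | 8 to 10 |

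So the number of ECGs in the DLT window that must follow consecutive-day dosing is 0 in Table 3 and 1 in each other table.

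**Step 3: how much exposure Day 8 could understate.** The documents give no half-life. The 12 h in SAP 4.1 is only a possible trigger for twice-daily dosing. Assume first-order linear PK, once-daily dosing, no auto-induction and no carry-over from Cycle 0. Exposure on day d relative to a single dose is

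A(d) = sum over dosing days x ≤ d of 2^(−24(d − x)/t½), with t½ in hours.

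Example at t½ = 24 h:
- Table 3, Day 8: 1 + 2^−5 + 2^−6 + 2^−7 = 1.055
- Table 3, Day 10: 1 + 2^−1 + 2^−2 + 2^−7 + 2^−8 + 2^−9 = 1.764
- Day 8 of unbroken daily dosing: 2 − 2^−7 = 1.992
- Ratios: 1.055/1.764 = 60% and 1.055/1.992 = 53%

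| Assumed t½ | Table 3 Day 8 | Table 3 Day 10 | Unbroken Day 8 | Day 8 / Day 10 | Day 8 / unbroken Day 8 |
|---|---|---|---|---|---|
| 6 h | 1.000 | 1.066 | 1.067 | 94% | 94% |
| 12 h | 1.001 | 1.313 | 1.333 | 76% | 75% |
| 24 h | 1.055 | 1.764 | 1.992 | 60% | 53% |
| 36 h | 1.201 | 2.107 | 2.635 | 57% | 46% |
| 48 h | 1.390 | 2.402 | 3.201 | 58% | 43% |

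The Day 8/Day 10 ratio stops falling at the long end because carry-over across the break begins to count. What remains on Day 8 from the Day 3 dose, 120 h earlier, is 2^(−120/t½): 0.1% at 12 h, 3% at 24 h and 18% at 48 h.

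**The case against.** The +2 window already allows the ECG on Day 9 or 10, and Day 8 is the fourth dose of Cycle 1. A reader might infer that this schedule never gets an ECG after consecutive dosing in the window. The documents do not support that. What stands is that such an ECG is optional, and that the dose before Day 8 was five days earlier.

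Table 4 is not visible and could fix the clock time, or the place within the window. It would not be expected to move a visit that the grid marks, but the sponsor should check it.

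A reader might also infer that QTc DLTs would be missed and the schedule would look safer than the others. That goes too far. SAP 12.1 does not limit DLTs to scheduled ECGs, so symptomatic events and unscheduled ECGs count. The Cycle 2 Day 3 ECG enters the QTcF categories of SAP 12.5, and the SRC weighs all available data.

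The strongest mitigant is in SAP 4.1: a new schedule may start no higher than the top total daily dose already through DLT evaluation. If that dose was cleared on the initial 2 weeks on/1 week off schedule, it already had an ECG at the 8th to 10th consecutive dose, with more accumulation than Table 3 produces. This stands, and it limits the exposed case to later escalation within the schedule.

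Three further inferences fail:
- The CXD1 rule ("A -2-day window is allowed for the assessments scheduled for the CXD1 visit") is in all five schedules, so it is not a weakness of this one. Table 3 is also the only intermittent schedule with a marked ECG after Cycle 1 on a consecutive-dose day.
- Nothing can be concluded about PK sample timing, because the governing footnotes are not in the public text.
- Mixing unlike Day 8 values affects only the overall column, since SAP 7 presents results by dose level and schedule.

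**Conclusion.** The point holds in a limited form. Table 3 permits but does not require an ECG after consecutive-day dosing inside the DLT window, while every other schedule requires one. A QTc effect that is asymptomatic and needs accumulation could therefore escape the scheduled Cycle 1 ECGs. The practical risk lies mainly in escalating this schedule, which is itself conditional, above doses already cleared on longer dosing blocks.

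The size cannot be settled from the documents. Over assumed half-lives of 6 to 48 h, Day 8 exposure runs from about 94% down to just under 60% of Day 10 exposure. With a short half-life the gap is negligible; from about 24 h it is material. The figures assume linear once-daily PK without auto-induction. The Protocol describes the drug as an in vitro enzyme inducer, so that last assumption is open. The ratios describe exposure only, because the documents give no exposure–QTc relation.

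**What to change.** Reconcile the Cycle 1 ECG day in Table 3 with its dosing calendar and with its own Cycle 2 Day 3 timing. The direct way is to require the Cycle 1 ECG in the part of the Day 8 (+2) window that follows consecutive doses, namely the third dosing day of the block (Day 10), and to align Table 4.

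This is a wording change and adds no ECG. It does have a cost. The ECG loses its two days of scheduling flexibility, and the CBC, vital signs and PK sample now marked at Cycle 1 Day 8 either move with it inside the same window or need a separate visit. The sponsor should state which.
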